1.0 TRIAL SUMMARY

Abbreviated Title	Pembrolizumab (MK-3475) in elderly patients with non-small cell lung cancer
Trial Phase and Type	Phase II, Interventional
Clinical Indication	First line treatment in PD-L1 positive advanced non-small cell lung cancer patients
Trial Identification	Sponsor Code: GECP 16/06; Short name: PEBEL
Type of control	Not applicable
Route of administration	Intravenous
Trial Blinding	Open label
Treatment Groups	1 group, Pembrolizumab (MK-3475) 200 mg, every 3 weeks
Number of trial subjects	82
Estimated enrollment period	12 months
Estimated duration of trial	The sponsor estimates that the trial will require approximately 4 years (1 year recruiting patients, 2 years of treatment and at least 1 year of follow up)
Duration of Participation	
Each subject will participate in the trial from the time the subject signs the Informed Consent Form (ICF) through the final protocol-specified contact. After a screening phase of up to 28 days (see Section 6.0), eligible subjects will receive assigned treatment on Day 1 of each 3-week (Q3W) dosing cycle.
 
Treatment with MK-3475 will continue until two years of therapy have been administered, documented disease progression, unacceptable adverse event(s), intercurrent illness that prevents further administration of treatment, investigator's decision to withdraw the subject, subject withdraws consent, noncompliance with trial treatment or procedure requirements, or administrative reasons.
 
MK-3475 treated subjects who attain a complete response may consider stopping trial treatment. These subjects will be eligible for re-treatment for up to one year with MK-3475 after experiencing disease progression at the discretion of the investigator if they meet the criteria for re-treatment; this will be designated the Second Course phase. After the end of treatment, each subject will be followed for a minimum of 30 days for adverse event monitoring (serious adverse events will be collected for up to 90 days after the end of treatment).
 
Subjects will have post-treatment follow-up for disease status, including initiating a non-study cancer treatment and experiencing disease progression, until death, withdrawing consent, or becoming lost to follow-up.

Estimated average length of treatment per patient	According to previous data of patients treated with Pembrolizumab, the estimated average length of the treatment is approximately 7 months

[figure not shown]
[figure not shown]
[figure not shown]
2.0 GENERAL INFORMATION

2.1 Trial Identification

Sponsor code: GECP 16/06

EudraCT: 2016-004353-32

[figure not shown]
Protocol title: "Survival, quality of life and self-reported outcomes of elderly patients with advanced non-small cell lung cancer (NSCLC), treated with pembrolizumab (MK-3475) in the first line setting"
PEBEL

2.3 Trial Diagram

Figure 1

2.4 Primary Objective(s) & Hypothesis(es)

- To determine the efficacy, in terms of overall survival at one year, of first-line treatment with Pembrolizumab (MK-3475) in elderly patients with advanced NSCLC expressing PD-L1.

Hypothesis: Patients older than 70 years with advanced Non-small cell Lung Cancer (NSCLC) expressing PD-L1, can be treated with Pembrolizumab (MK-3475) in the first line setting, with an overall survival at one year of 50% at least. This result supposes an improvement of 4 months in the median respect of historical data.

2.5 Secondary Objective(s) & Hypothesis(es)

- To evaluate changes in health-related quality of life in responder and non-responder patients older than 70 years with advanced non-small cell lung cancer (NSCLC) expressing PD-L1, treated with pembrolizumab (MK-3475) in the first line setting, according to the QLQ-C30, the LCSS and the QLQ-ELD14 questionnaires.
- To evaluate the impact on functional, cognitive and nutritional geriatric assessments of patients older than 70 years with advanced non-small cell lung cancer (NSCLC), expressing PD-L1, treated with pembrolizumab (MK-3475) in the first line setting
- To describe the Objective Response Rate (ORR), and the Progression-free Survival (PFS), according to RECIST criteria v. 1.1 of the first-line treatment with pembrolizumab (MK-3475) in elderly patients with advanced NSCLC expressing PD-L1.
- To assess the median disease-specific survival (DSS) and the Overall Survival rate at 2 years.
- To describe the safety and tolerability profile of first-line pembrolizumab (MK-3475) in previously untreated elderly patients with advanced NSCLC expressing PD-L1.

Hypothesis: Treatment with Pembrolizumab (MK-3475) in the first line setting of patients older than 70 years with advanced non-small cell lung cancer (NSCLC) expressing PD-L1 can maintain or improve health-related quality of life, according to the QLQ-C30, the LCSS and the QLQ-ELD14 questionnaires. Also, the treatment can maintain or improve functional, cognitive, and nutritional geriatric assessments.

2.6 Exploratory Objective

- Description of PD-L1 expression in previously untreated elderly patients with advanced NSCLC.

Approximately 60% of the patients evaluated for being included in this trial will express PD-L1.

2.7 Trial Study centers

This trial will be carried out in around 10 participant study sites in Spain.

2.8 Trial duration

Approximately 4 years (1 year recruiting patients, 2 years of treatment and at least 1 year of follow up)

3.0 BACKGROUND & RATIONALE

3.1 Background

Refer to the Investigator's Brochure (IB)/approved labeling for detailed background information on MK-3475.

3 [REDACTED]

[figure not shown]
[figure not shown]

[figure not shown]
[figure not shown]

3.3 Preclinical and Clinical Trial Data

Refer to the Investigator's Brochure for Preclinical and Clinical data.

11. **What is the primary purpose of the *Journal of Clinical Endocrinology and Metabolism*?**

For more information, contact the Office of the Vice President for Research and Economic Development at [contact] or [contact].

For more information, contact the Office of the Vice President for Research and Economic Development at [contact] or [contact].

[figure not shown]
For more information, visit www.ams.org.

10. *Journal of the American Statistical Association*, 1990, 85, 200-209.

For more information, contact the Office of the Vice President for Research and Economic Development at [contact] or [contact].

1. **What is the primary purpose of the study?** The study aims to evaluate the effectiveness of a new treatment for hypertension in a diverse population.

11. **What is the primary purpose of the *Journal of Clinical Endocrinology and Metabolism*?**

4.0 METHODOLOGY

4.1 Eligibility Criteria

4.1.1 Subject Inclusion Criteria

1. Patients with histological or cytological documented stage IIIB or IV squamous and non-squamous non-small-cell lung cancer previously untreated.
2. EGFR and ALK have to be wild-type.

3. The subject must be willing and able to provide written informed consent/assent for the trial.
4. Patients must be aged ≥ 70 years, on day of signing informed consent.
5. Measurable disease (at least 1 lesion) based on RECIST criteria v1.1. Patients will not be eligible if this lesion was irradiated before inclusion.
6. Be willing to provide tissue from a newly obtained core or excision biopsy of a tumor lesion. Newly-obtained is defined as a specimen obtained up to 6 weeks (42 days) prior to initiation of treatment on Day 1. Subjects for whom newly-obtained samples cannot be provided (e.g. inaccessible or subject safety concern) may submit an archived specimen only upon agreement from the Sponsor.
7. PD-L1 expression $\geq 1\%$
8. Have a performance status of 0 or 1 on the ECOG Performance Scale.
9. Screening laboratory values must meet the following criteria (Table 1), all screening labs should be performed within 8 days of treatment initiation.

Table 1 Adequate Organ Function Laboratory Values

SYSTEM	Laboratory value
Hematological	
Absolute neutrophil count (ANC)	$\geq 1,500 / \mu\text{L}$
Platelets	$\geq 100,000 / \mu\text{L}$
Hemoglobin	$\geq 9 \text{ g/dL}$ or $\geq 5.6 \text{ mmol/L}$ without transfusion or EPO dependency (within 7 days of assessment)
Renal	
Serum creatinine OR Measured or calculated creatinine clearance (Cockcroft–Gault formula) (GFR can also be used in place of creatinine or CrCl)	$\leq 1.5 \times$ upper limit of normal (ULN) OR $\geq 50 \text{ mL/min}$ for subject with creatinine levels $> 1.5 \times$ institutional ULN
Hepatic	
Serum total bilirubin	$\leq 1.5 \times$ ULN OR
	Direct bilirubin \leq ULN for subjects with total bilirubin levels > 1.5 ULN
AST (SGOT) and ALT (SGPT)	$\leq 2.5 \times$ ULN OR $\leq 5 \times$ ULN for subjects with liver metastases

Albumin	>2.5 mg/dL
Coagulation	
International Normalized Ratio (INR) or Prothrombin Time (PT)	≤1.5 X ULN unless subject is receiving anticoagulant therapy as long as PT or PTT is within therapeutic range of intended use of anticoagulants
Activated Partial Thromboplastin Time (aPTT)	≤1.5 X ULN unless subject is receiving anticoagulant therapy as long as PT or PTT is within therapeutic range of intended use of anticoagulants

10. Male subjects of childbearing potential must agree to use an adequate method of contraception, starting with the first dose of study therapy through 120 days after the last dose of study therapy.

Note: Abstinence is acceptable if this is the usual lifestyle and preferred contraception for the subject.

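### The albumin entry limit in Table 1 is given in mg/dL, so as written it excludes nobody; the unit appears to be an error and needs confirmation

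*Combined protocol and SAP*

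**What the plan says.** Section 4.1.1, inclusion criterion 9, states: "Screening laboratory values must meet the following criteria (Table 1), all screening labs should be performed within 8 days of treatment initiation". The table it refers to is headed "Table 1 Adequate Organ Function Laboratory Values", and its albumin row, listed with the hepatic tests, reads "Albumin >2.5 mg/dL".

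Albumin is not mentioned anywhere else in the readable text, so nothing corrects or overrides the unit. The only other row of Table 1 stated as a mass concentration is hemoglobin, with a minimum of 9 g/dL and an alternative of 5.6 mmol/L.

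**The concern.** Criterion 9 is mandatory, so each row of Table 1 decides who may enter. An albumin limit in mg/dL lies far below any value a living patient would show. The row therefore does no work in a table meant to establish adequate organ function.

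The two possible readings give different answers for the same person. Take an albumin of 1.5 g/dL, which is 1500 mg/dL. Under the printed text that patient qualifies; under a g/dL reading the patient does not. The trial plans around 10 sites (section 2.7), and eligibility should not depend on whether each of them corrects the text silently. Monitoring against the printed text could not flag such a patient, and an edit check coded literally would never fire.

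The definition of the enrolled population carries some weight here. The trial has a single arm, its survival result is judged against historical data (sections 2.4 and 8.0), it enrols patients aged 70 or over, and nutritional assessment is among its secondary objectives (section 2.5).

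**Working it through.** **Inputs**
- Written limit: above 2.5 mg/dL (section 4.1.1, Table 1).
- Unit conversions: 1 g/dL = 1000 mg/dL = 10 g/L.
- Patient albumin: not given in the documents. Assumed to run from about 1 g/dL (severe hypoalbuminaemia) to 5 g/dL (upper normal).
- Hemoglobin limits: 9 g/dL and 5.6 mmol/L (same table).
- Hemoglobin molar mass per monomer: not given in the documents. Assumed 16.114 g/mmol.

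No sample-size, power or error-rate figure enters this point, so there is no design figure to reproduce.

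**Step 1. Convert the written limit.** 2.5 mg/dL ÷ 1000 = 0.0025 g/dL; 0.0025 × 10 = 0.025 g/L.

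**Step 2. Compare the limit with patient values.** Ratio = (albumin in g/dL × 1000) ÷ 2.5.

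| Assumed albumin (g/dL) | In mg/dL | Multiple of the written limit |
|---|---|---|
| 1.0 | 1000 | 400 |
| 1.5 | 1500 | 600 |
| 2.0 | 2000 | 800 |
| 2.5 | 2500 | 1000 |
| 3.5 | 3500 | 1400 |
| 5.0 | 5000 | 2000 |

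The smallest ratio is 400. To fail the printed criterion, a patient would need an albumin of 0.0025 g/dL or less, which is 1/400 of the lowest value assumed. The conclusion does not depend on where in the range a patient falls.

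**Step 3. Size of the gap between the two readings.** The same numeral read in g/dL is 2.5 × 1000 = 2500 mg/dL, or 25 g/L. The readings differ by 2500 ÷ 2.5 = 1000. That factor is exact between the units; against assumed patient values the multiple runs from 400 to 2000.

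**Step 4. Check the neighbouring unit.** Hemoglobin: 9 g/dL = 90 g/L; 90 ÷ 16.114 = 5.59 mmol/L, which matches the stated 5.6. The table handles g/dL correctly in that row, so the oddity is confined to albumin.

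**The case against.** The best opposing case is that this is a probable unit slip with little practical effect.

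- **Sites would probably read g/dL.** Nothing in the documents shows that any site would apply the row literally, or that an eCRF check on albumin exists. This stands. A reader might infer that sites will in fact enrol different populations, or that the one-year survival result is compromised. The documents give no basis for estimating how many of the 82 planned patients would fall between the two limits, so neither inference is supported.
- **Other criteria also screen frail patients.** Exclusion 11 lets the investigator exclude for a laboratory abnormality that might confound results or make participation contrary to the patient's interest. ECOG status must be 0 or 1, and exclusion 13 covers functional dependence and short life expectancy from comorbidity. Table 1 also limits INR or PT, which partly reflects liver synthesis, so albumin is not the only hepatic-function safeguard. This stands against any suggestion that severely hypoalbuminaemic patients enter unscreened. None of these criteria sets an albumin value, so none repairs the row.
- **The text may have been misread from the PDF.** The extraction contains spurious content elsewhere, the section 5.0 flow chart is not visible, and much of section 6 is redacted. A misread unit cannot be fully excluded. The row itself is well formed, however, and shows no sign of damage or redaction.
- **Correcting the limit could turn enrolled patients into violations.** A reader might infer that anyone below the corrected limit was wrongly enrolled. That does not follow, because such a patient met the criterion in force at entry.

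**Conclusion.** The albumin criterion is wrong as written. It is an operative entry rule that no patient can fail, on the assumption that patient albumin lies between about 1 and 5 g/dL. The discrepancy is a factor of 1000 between the printed unit and the one the table uses for hemoglobin. A unit error is the likeliest explanation, but only the sponsor can confirm the intended limit.

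The consequence is ambiguous eligibility for patients with very low albumin, and no clear basis for calling such an entry a deviation. The number affected is unknown and probably small. The sample size and the primary analysis method do not depend on this row.

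**What to change.** The sponsor should confirm the intended albumin limit and correct the unit in Table 1. If the numeral 2.5 is as intended, the matching unit is g/dL, equivalent to 25 g/L; printing both units, as the hemoglobin row does, would remove doubt. Any eCRF check on albumin should use the confirmed value and unit. It is also worth looking at the PDF page to rule out a reading error.

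Patients already enrolled whose screening albumin falls below the confirmed limit can be counted and described. They should not be logged automatically as eligibility deviations; their status is for the sponsor to decide, given that they complied with the text then in force.

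The cost is a one-line protocol correction and, where an edit check exists, its alignment. A few later candidates with very low albumin might become screen failures.

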4.1.2 Subject Exclusion Criteria

The subject must be excluded from participating in the trial if the subject:

1. Is currently participating and receiving study therapy or has participated in a study of an investigational agent and received study therapy or used an investigational device within 4 weeks of the first dose of treatment.
2. Has a diagnosis of immunodeficiency or is receiving systemic steroid therapy at a dose over 10 mg of prednisone or equivalent, or any other form of immunosuppressive therapy within 7 days prior to the first dose of trial treatment.
3. Has a known history of active TB (Bacillus Tuberculosis)
4. Hypersensitivity to Pembrolizumab or any of its excipients.
5. Has had any prior anti-cancer therapy for his or her metastatic NSCLC. In the case of patients who have progressed to a metastatic stage after having been treated for early stage NSCLC, chemotherapy or radiation therapy as part of this previous treatment is allowed, provided they have been completed more than three months ago. Patients who received adjuvant or neoadjuvant treatment or both for early stages will be

eligible for this trial. All adverse events related to these previous treatments must have recovered (i.e., \leq Grade 1 or at baseline).

6. Has had any previous malignancy (except non melanoma skin cancer, and cancer in situ of: bladder, gastric, colon, cervical/dysplasia, melanoma, breast), unless a complete remission was achieved at least 2 years prior to study entry and no additional therapy is required or anticipated to be required during the study period.
7. Has known active central nervous system (CNS) metastases and/or carcinomatous meningitis. Subjects with previously treated brain metastases may participate if they are stable (without evidence of progression by imaging for at least four weeks prior to the first dose of trial treatment and any neurologic symptoms have returned to baseline), have no evidence of new or enlarging brain metastases, and are not using steroids at a dose over 10 mg of prednisone or equivalent, for at least 7 days prior to trial treatment. This exception does not include carcinomatous meningitis which is excluded regardless of clinical stability.
8. Has active autoimmune disease that has required systemic treatment in the past 2 years (i.e. with use of disease modifying agents, corticosteroids or immunosuppressive drugs). Replacement therapy (eg., thyroxin, insulin, or physiologic corticosteroid replacement therapy for adrenal or pituitary insufficiency, etc.) is not considered a form of systemic treatment.
9. Has a history of (non-infectious) pneumonitis that required steroids or current pneumonitis.
10. Has an active infection requiring systemic therapy.
11. Has a history or current evidence of any condition, therapy, or laboratory abnormality that might confound the results of the trial, interfere with the subject's participation for the full duration of the trial, or is not in the best interest of the subject to participate, in the opinion of the treating investigator.
12. Has known psychiatric or substance abuse disorders that would interfere with cooperation with the requirements of the trial.
13. Has any geriatric exclusion criteria:
 - advanced dementia (GDS ranking ≥ 6)
 - moderate or severe functional dependence (Barthel Index ≤ 35)
 - Life expectancy less than one year, due to co-morbidities other than lung cancer.

14. Has a known history of Human Immunodeficiency Virus (HIV) (HIV 1/2 antibodies).
15. Has known active Hepatitis B (e.g., HBsAg reactive) or Hepatitis C (e.g., HCV RNA [qualitative] is detected).
16. Has received a live vaccine within 30 days of planned start of study therapy.

Note: Seasonal influenza vaccines for injection are generally inactivated flu vaccines and are allowed; however intranasal influenza vaccines (e.g., Flu-Mist®) are live attenuated vaccines, and are not allowed.

17. Evidence of interstitial lung disease.

4.2 Trial Treatments

The treatment to be used in this trial is outlined below:

Table 2. Trial Treatment

Drug	Dose/Potency	Dose Frequency	Route of Administration	Regimen/Treatment Period
Pembrolizumab (MK-3475)	200 mg	Q3W	IV, infusion	Day 1 of each 3 week cycle

[figure not shown]
The treatment must start as soon as possible after receiving PD-L1 positive results and no more than 7 days. The treatment will continue until disease progression, unacceptable toxicity, consent withdrawal, or until the treatment is administered during two years, whichever occurs first.

Details on preparation and administration of pembrolizumab (MK-3475) are provided in the Drug Supply Manual.

4.2.1 Dose Selection/Modification

Dose Selection

The rationale for selection of the dose to be used in this trial is provided in Section 3.5 – Background and Rationale.

4.2.2 Timing of Dose Administration

Trial treatment should be administered on Day 1 of each cycle (QW3) after all procedures/assessments have been completed as detailed on the Trial Flow Chart (Section 5.0). Trial treatment may be administered up to ± 3 days the scheduled Day 1 of each cycle due to administrative or personal reasons.

All trial treatments will be administered on an outpatient basis.

Pembrolizumab (MK-3475) 200 mg will be administered as a 30 minute IV infusion every 3 weeks. Sites should make every effort to target infusion timing to be as close to 30 minutes as possible. However, given the variability of infusion pumps from site to site, a window of -5 minutes and +10 minutes is permitted (i.e., infusion time is 30 minutes: -5 min/+10 min).

The Drug Supply Manual contains specific instructions for the preparation of the pembrolizumab infusion fluid and administration of infusion solution.

[REDACTED]

[REDACTED]

[REDACTED]

[REDACTED]

4.2.4 Trial Blinding/Masking

This is an open-label trial; therefore, the Sponsor, investigator and subject will know the treatment administered.

4.3 Concomitant Medications/Vaccinations (allowed & prohibited)

Medications or vaccinations specifically prohibited in the exclusion criteria are not allowed during the ongoing trial.

If there is a clinical indication for one of these or other medications or vaccinations specifically prohibited during the trial, discontinuation from trial therapy or vaccination may be required.

The investigator should discuss any questions regarding this with the sponsor of the study. The final decision on any supportive therapy or vaccination rests with the investigator and/or the subject's primary physician.

A series of 15 horizontal black bars of varying lengths, starting with a very long bar and ending with a very short bar. The bars are arranged vertically, with the longest bar at the top and the shortest at the bottom. The lengths of the bars decrease progressively from top to bottom.

4.6 Subject Withdrawal/Discontinuation Criteria

4.6.1 Subject Withdrawal

Subjects may withdraw consent at any time for any reason or be dropped from the trial at the discretion of the investigator should any untoward effect occur. In addition, a subject may be withdrawn by the investigator or the Sponsor if enrollment into the trial is inappropriate, the trial plan is violated, or for administrative and/or other safety reasons.

Specific details regarding discontinuation or withdrawal are provided in Section 6.10.

A subject must be discontinued from the trial for any of the following reasons:

- The subject or legal representative (such as a parent or legal guardian) withdraws consent.
- Confirmed radiographic disease progression

Note: A subject may be granted an exception to continue on treatment with confirmed radiographic progression if clinically stable or clinically improved.

- Unacceptable adverse experiences
- Intercurrent illness that prevents further administration of treatment
- Investigator's decision to withdraw the subject
- Noncompliance with trial treatment or procedure requirements
- The subject is lost to follow-up

- Completed 24 months of uninterrupted treatment with pembrolizumab or 35 administrations of study medication, whichever is later.

Note: 24 months of study medication is calculated from the date of first dose. Subjects who stop pembrolizumab after 24 months may be eligible for up to one year of additional study treatment if they progress after stopping study treatment provided they meet the requirements detailed in Section 6.12.

- Administrative reasons

The End of Treatment and Follow-up visit procedures are listed in Section 5 (Protocol Flow Chart). After the end of treatment, each subject will be followed for 30 days for adverse event monitoring (serious adverse events will be collected for 90 days after the end of treatment as described in Section 7.6). Subjects who discontinue for reasons other than progressive disease will have post-treatment follow-up for disease status until disease progression, initiating a non-study cancer treatment, withdrawing consent or becoming lost to follow-up. After documented disease progression each subject will be followed by telephone for overall survival until death, withdrawal of consent, or the end of the study, whichever occurs first.

